- Continuous repeated measures data collected at more than one visit will be analysed using a constrained longitudinal data analysis technique (Liang 2000). The outcome (dependent variable) will consist of the baseline and postbaseline values. The model will assume a common baseline mean across the two treatment arms due to random allocation. It will incorporate time point (study visit) as a categorical variable, thus it will not assume a specific trajectory over time. In addition to study visit, the model will include treatment as the main factor and the treatment by study visit interaction. The variancecovariance among the repeated measurements will be defined as unstructured. In the case of non-convergence, we will consider alternative structures (first-order autoregressive, Toeplitz, compound symmetry). Using this model, study participants with a missing baseline or a missing postbaseline value will be included in the analysis but study participants with no outcome values will be excluded. This model will yield unbiased results when the outcome data are Missing At Random. We will report the estimate and two-sided confidence interval of the absolute difference between two treatment groups in the change from baseline to 3 months and 6 months postbaseline (if applicable). Before fitting this model, the distribution of the outcome will be explored. In addition, we will examine if there are potential violations of underlying model assumptions (e.g. residuals). As a result, we may apply an appropriate transformation (e.g. log-transformation) before fitting the final model.
- Binary data will be analysed using a logistic regression model. We will report
 the estimate and two-sided confidence interval of the odds ratio between the
 two treatment groups.
- Categorical data will be analysed using an ordinal logistic regression model.
 We will report the estimate and two-sided confidence interval of the odds ratio between the treatment groups.

Details of which model will be used for each of the primary, key secondary, and secondary outcomes can be found in Appendix 3.

Compliance

See Table 4 in **Appendix 4**.

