7.1.1 Multiple testing

The primary outcome at day 180 will be evaluated using the two-sided 5% level of significance.

Multiple testing for the key secondary outcomes related to corneal nerve parameters at day 180 will be assessed using the Benjamini-Hochberg stepwise method with a false discovery rate of 5% for: corneal nerve fibre density (CNFD), corneal nerve branch density (CNBD), central corneal sensitivity thresholds to room temperature, and central corneal sensitivity thresholds to cooled temperature. For these key secondary outcomes at day 180, we will report the multiplicity adjusted p-values.

For all other post-baseline time points and outcomes, we will report multiplicity unadjusted p-values. Given the large number of statistical tests, the probability of finding at least one false positive finding will be close to 100%. For this reason, we will exercise caution and in addition to p-values, associations will be interpreted based on the magnitude and direction of the association and width of the 95% confidence intervals.

All tests will be performed two-sided, and we will report two-sided 95% confidence intervals.

8. Sensitivity Analyses

Additional sensitivity analyses will be performed for the outcomes linked to the primary and key secondary aims for the following dataset:

- Dataset excluding participants deemed non-compliant (see definition in Section 6.3).

9. QC Plans

Source data verification of the data entered on REDCap was performed by the Principal Investigator (PI). Data was manually checked for accuracy from the source worksheets/original digital data record, for all participants, for the primary outcome (CNFL) and key secondary outcomes (CNFD, CNBD, central corneal sensitivity thresholds to room temperature, and central corneal sensitivity thresholds to cooled temperature). In addition, a subset of data comprising at least 20% of the full dataset,

was randomly selected by the PI for verification, to ensure that the observations and findings are recorded correctly and completely. Data found as incorrectly entered were verified against the original source documents, corrected on REDCap and recorded accordingly.

10. Programming Plans

A list of all planned tables and figures and their templates can be found in Appendix 4.

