Habitual distance visual acuity (LogMAR) - Right eye - Left eye								
Intraocular pressure (mmHg) - Right eye - Left eye								
Diabetic retinopathy in the worse eye, n (%) - None - Mild - Moderate - Severe - Proliferative								
Diabetic macular oedema in the worse eye, n (%) - None - Macular oedema - Clinically significant macular oedema								
Blood biochemistry								
HbAıC (mmol/mol)								
Cholesterol (mmol/L)								
HDL (mmol/L)								
LDL (mmol/L)								
Creatinine (µmol/L)								
Vitamin B12 (pmol/L)								
Folate (nmol/L)								

^{*} Mean and standard deviation unless stated otherwise.

[†] p-values are not adjusted for multiple testing.

Abbreviations: HbAıC, haemoglobin Aıc; HDL, high-density lipoproteins; LDL, low density lipoproteins.

Changes from the planned analysis in the Statistical Analysis Plan

- 1. A sensitivity analysis was performed for outcomes with substantial imbalance at baseline either in the mean (continuous outcomes) or geometric mean (log base e transformed outcomes) between groups. The imposed constraint of balance at baseline of the constrained longitudinal data analysis model was removed by adjusting the primary model for the interaction between baseline and treatment in addition to the factors already part of the longitudinal data analysis model.
- 2. We had intended to analyse categorical and binary variables using (ordinal) logistic regression analysis. However, this model could not be fitted due to the distribution of the data within and between groups. Instead, for categorical and binary variables, change from baseline at the study endpoint for each participant was categorised as negative change, positive change, or no change. Fisher's exact test was used to compare the proportions of participants between treatment groups. For MDNS scores, in changing from analysing this parameter as a continuous variable to a categorical variable, the class of neuropathy (class 0–3 as defined by the MDNS) was derived as the highest score from the clinical scoring or neurophysiology component.

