Data reported as the number of participants with the medications. Concomitant medications are categorised using the United States Pharmacopeia (USP; United States Pharmacopeial Convention) Drug Classifications 2019, published on https://www.usp.org/

Table S2. Compliance outcomes using systemic fatty acid profiles (Intention-To-Treat sample)

	0	mega-3 PUF	As		Placebo	Omega-3 PUFAs vs Placebo		
	Baseline (n=21)	Day 180 (n=21)	Change from baseline (n=21)	Baseline (n=22)	Day 180 (n=19)	Change from baseline (n=19)	Estimate (95% CI) (n =43)	p- value ^a
Omega-3 Index	4.9 (0.8)	8.2 (1.7)	3.3 (1.8)	4.6 (1.0)	4.8 (1.3)	0.12 (1.0)	3.3 (2.4,4.2)	< 0.001
EPA, %	0.6 (0.2)	2.11 (0.7)	1.5 (0.8)	0.6 (0.2)	0.7 (0.4)	0.08 (0.4)	1.4 (1.1,1.8)	< 0.001
DHA, %	1.9 (0.5)	3.0 (0.7)	1.1 (0.7)	1.8 (0.7)	1.8 (0.7)	0.01 (0.5)	1.1 (0.7,1.5)	< 0.001
Total omega-6, %	25.0 (4.7)	25.8 (3.4)	0.8 (4.1)	26.9 (2.8)	28.3 (2.6)	1.52 (4.0)	-2.1 (-3.9,-0.3)	0.023 b
Total omega-9, %	20.9 (5.0)	21.1 (2.5)	0.3 (5.6)	21.0 (3.8)	20.5 (1.9)	-1.26 (3.5)	0.7 (-0.7,2.0)	0.34
Omega- 6:omega-3 ratio	6.1 (1.7)	3.7 (0.9)	-2.4 (2.0)	7.2 (1.8)	7.3 (1.8)	0.2 (1.9)	-3.5 (-4.3,-2.6) ^c	<0.001°

Data are reported as mean and standard deviation. DHA=docosahexaenoic acid. EPA=eicosapentaenoic acid. PUFA=polyunsaturated fatty acid.

^a p-values are not adjusted for multiple testing.

^b In a sensitivity analysis adjusting for imbalance at baseline, the treatment effect for total omega-6 is -0.59 (-3.09,1.92) %; unadjusted p-value = 0.65.

^c In a sensitivity analysis adjusting for imbalance at baseline, the treatment effect for omega-6:omega-3 ratio is -2.54 (-3.77,1.32) %; unadjusted p-value <0.001.

Table S3. Safety outcome: Summary of adverse events (Safety sample)

	Omega-3 PUFAs (n=21)	Placebo (n=22)	Omega-3 PUFAs vs Placebo p- value
Summary of all adverse events ^a			value
At least one AE or SAE, n [%]	9 [43%]	7 [32%]	0.54
At least one AE, n [%]	9 [43%]	6 [27%]	0.35
At least one SAE, n [%]	0 [0%]	1 [5%]	1.0
Unrelated adverse events ^b			
Haematologic	0	1	
Ocular			
Posterior segment/retinal condition (not associated with diabetes)	0	2	
Light sensitivity/headache	1	2	
Respiratory symptoms	4	2	
Gastrointestinal (unrelated SAE)	0	1	
Musculoskeletal pain/cramping	1	1	
Change in blood glucose control	0	1	
Dermatological: rash or skin changes	2	0	
Cardiovascular: heart palpitations	1	0	
Immunologic: unrelated allergic reaction	1	0	
Potentially-related adverse events ^b			
Gastrointestinal: nausea ^c	2	1	

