AE=adverse event. SAE=serious adverse event. PUFA=polyunsaturated fatty acid.

^aData are reported as number of individuals with at least one AEs.

^bData are reported as the number of adverse events.

^cGastrointestinal effects were deemed to be possibly related to the treatment due to biological plausibility.

Table S4. Corneal structure (*in vivo* confocal microscopy) and function (non-contact aesthesiometry) outcomes baseline, day 90, and day 180 (Intention-To-Treat sample)

			Omega-3 PU	FAs				Placebo			Omeg	ga-3 PUF	As vs Placeb	0
	Baselin e (n=21)	Day 90 (n=19)	Change from baseline at day 90 (n=19)	Day 180 (n=21)	Change from baseline at day 180 (n=21)	Baselin e (n=22)	Day 90 (n=18)	Change from baseline at day 90 (n=18)	Day 180 (n=19)	Change from baseline at day 180	Estimate (95% CI) Day 90 (n=43)	p- value	Estimate (95% CI) Day 180 (n=43)	p- value a
Central CNFL (mm/mm ²)	11·49 (3·34)	13·09 (2·45)	1.62 (1.92)	13·55 (3·58)	2.06 (1.73)	12·38 (3·21)	12·30 (3·79)	-0·15 (1·12)	11·41 (3·66)	-0·72 (1·68)	1·80 (0·83,2·78)	<0.00	2·70 (1·64,3·75)	<0.00
Central CNFD (nerves/mm ²)	19·93 (7·72)	22·45 (5·84)	2.78 (3.99)	23·41 (8·08)	3.48 (4.15)	20·27 (7·36)	20·92 (8·32)	0.49 (3.19)	18·45 (7·57)	-1·57 (4·02)	2·41 (0·26,4·56)	0.028	4·98 (2·51,7·44)	<0·00 1
Central CNBD (beanches/mm²)	19·69 (10·76)	24·92 (7·46)	5.65 (8.23)	27·06 (13·59)	7.37 (6.34)	23·48 (10·27)	21·58 (11·98)	-2·84 (6·39)	19·54 (12·64)	-3·68 (7·35)	7·31 (3·01,11·6 1)	0.001	11·23 (7·01,15·4 5)	<0·00 1
Peripheral CNFL (mm/mm ²)	5·09 (2·82)	4·40 (2·34)	-0·92 (2·19)	4·83 (2·23)	-0·26 (2·58)	5·20 (2·56)	4.47 (2.42)	-0.52 (2.09)	3·39 (2·49)	-1·90 (2·65)	-0·20 (- 1·35,0·94)	0.73	1.51 $(0.24, 2.77)$	0.020
Central corneal sensitivity threshold to room temperature (mbar), median	0·47 (0·38 - 0·75)	0·47 (0·25 - 0·80)	-0·15 (- 0·20 - 0·12)	0·38 (0·25 - 0·60)	-0·12 (- 0·20 0·00)	0·30 (0·28 - 0·45)	0·36 (0·25 - 0·57)	0·01 (-0·00 - 0·20)	0·30 (0·22 - 0·62)	0·12 (- 0·03 - 0·20)	0·73 (0·50,1·04) _{b,c}	0.084 c	0.68 (0.45,1.02) _{b,c}	0.061 c
(IQR) b Central corneal sensitivity threshold to cooled temperature (mbar), median	0·43 (0·30 - 0·70)	0·40 (0·22 - 0·68)	-0·07 (- 0·22 - 0·05)	0·35 (0·22 - 0·60)	-0·07 (- 0·20 - 0·03)	0·32 (0·15 - 0·47)	0·36 (0·20 - 0·60)	0·09 (0·00 - 0·20)	0·40 (0·20 - 0·52)	0·05 (- 0·00 - 0·20)	0·73 (0·48,1·12) b,c	0·15c	0.68 (0.45,1.04) b,c	0.077 c

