(IQR) ^b Central corneal dendritic cell density (cells/mm ²), median (IQR) ^b	19·79 (10·42 - 34·38)	31·25 (17·19 - 45·83)	6·77 (-6·77 - 15·63)	30·21 (16·15 - 44·79)	7·81 (-3·65 - 19·79)	37·76 (18·23 - 88·02)	34·64 (15·10 - 71·35)	-8·07 (- 20·31 0·52)	21·88 (16·67 - 55·73)	-2·08 (-11·46 - 15·10)	2·22 (1·32,3·75) b,c	0·003 0°	2·65 (0·90,7·79) b,c	0.077 c

		Omeg	a-3 PUFAs (c	ontinued)			Pla	cebo (continu	ed)		Omega-3 Pl	UFAs vs	Placebo (con	tinued)
	Baselin e (n=21)	Day 90 (n=19)	Change from baseline at day 90 (n=19)	Day 180 (n=21)	Change from baseline at day 180 (n=21)	Baselin e (n=22)	Day 90 (n=18)	Change from baseline at day 90 (n=18)	Day 180 (n=19)	Change from baseline at day 180 (n=19)	Estimate (95% CI) Day 90 (n=43)	p- value	Estimate (95% CI) Day 180 (n=43)	p- value a
Peripheral corneal dendritic cell density (cells/mm ²), median (IQR) ^b	69·53 (43·75 - 124·22	64·84 (46·09 - 119·53)	5·47 (-8·59 - 18·75)	66·41 (42·19 - 82·03)	-2·34 (- 46·88 - 6·25)	105·08 (76·56 - 187·50)	94·14 (45·31 - 151·56)	-11·33 (- 41·41 - 17·97)	75·00 (60·94 - 135·16)	-10·16 (-40·62 - 10·94)	2·18 (0·78,6·06) b,c	0·14 ^c	2·03 (0·73,5·62) b,c	0·18°
Peripheral corneal sensitivity threshold to room temperature (mbar), median (IQR) ^b	0·62 (0·35 - 0·95)	0·55 (0·43 - 0·80)	-0·05 (- 0·20 - 0·10)	0·50 (0·25 - 0·88)	-0·08 (- 0·38 - 0·20)	0·44 (0·28 - 0·52)	0·50 (0·30 - 0·65)	0·07 (-0·03 - 0·18)	0·45 (0·28 - 0·75)	0·23 (- 0·17 - 0·28)	0·73 (0·46,1·18) b,c	0·20°	0·75 (0·46,1·21) b,c	0·23°
Peripheral corneal sensitivity threshold to cooled temperature (mbar), median (IQR) ^b	0·52 (0·28 - 0·70)	0·45 (0·40 - 0·73)	-0·05 (- 0·15 0·02)	0·32 (0·25 - 0·65)	-0·10 (- 0·27 - 0·13)	0·36 (0·28 - 0·45)	0·43 (0·25 - 0·65)	0·03 (-0·12 - 0·33)	0·35 (0·30 - 0·55)	0·02 (- 0·08 - 0·12)	0.96 (0.56,1.63) b,c	0.87°	0·87 (0·58,1·32) b,c	0.51°

Mean and standard deviation, unless stated otherwise. All values are derived from examination of the right eye of all participants. CNBD=corneal nerve branch density. CNFD=corneal nerve fibre density. CNFL=corneal nerve fibre length. PUFA=polyunsaturated fatty acid.

^a p-values are not adjusted for multiple testing.
^b Descriptive data are presented as median and interquartile range; estimates are presented as geometric mean ratio of the change from baseline in Omega-3 PUFAs vs Placebo at day 180

^c Estimate and 95% CI after accounting for imbalance at baseline in the statistical analysis model.

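### Table S4 shows only the unplanned, unconstrained model for both corneal sensitivity thresholds, although the changes section calls that model a sensitivity analysis

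*Combined protocol and SAP*

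**What the plan says.** SAP Section 6 (Statistical procedures) specifies a constrained longitudinal data analysis for continuous repeated outcomes: "The model will assume a common baseline mean across the two treatment arms due to random allocation". SAP Appendix 3 assigns the repeated measures model to both central corneal sensitivity thresholds. SAP Section 7 (Multiple testing) makes them two of four key secondary outcomes, with Benjamini-Hochberg-adjusted p-values to be reported at day 180. The only extra dataset planned in SAP Section 8 is: "Dataset excluding participants deemed non-compliant (see definition in Section 6.3".

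Item 1 of the section on changes from the planned analysis then reports: "A sensitivity analysis was performed for outcomes with substantial imbalance at baseline either in the mean" or geometric mean. In that analysis "The imposed constraint of balance at baseline of the constrained longitudinal data analysis model was removed by adjusting the primary model". No size of imbalance is given as the trigger.

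The tables use this model in two ways.

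- **Table S2 (fatty acids):** the planned estimate stands in the table and the other result in a footnote: "In a sensitivity analysis adjusting for imbalance at baseline, the treatment effect for total omega-6 is -0.59 (-3.09,1.92").
- **Table S4 (corneal outcomes):** for both central thresholds, at days 90 and 180, the estimate and the p-value carry footnote c: "Estimate and 95% CI after accounting for imbalance at baseline in the statistical analysis model". The room-temperature result at day 180 is "0.68 (0.45,1.02"), p=0.061. The cooled result is 0.68 (0.45 to 1.04), p=0.077. No constrained estimate is shown for either.

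**The concern.** A sensitivity analysis should sit beside the planned result, not stand in for it. In Table S4 a reader sees two key secondary outcomes only under a model whose use was triggered by the observed baseline imbalance.

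The choice of model matters when the arms differ at baseline. The constrained model treats the gap as chance and carries forward only the part that baseline predicts. The unconstrained model subtracts the whole gap. The arm that starts higher is therefore credited with a fall that would partly be expected from regression to the mean. Here omega-3 starts with higher (less sensitive) thresholds, so the printed estimates are likely to look more favourable to omega-3 than the planned ones would.

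**Working it through.** **1. Which model is the unplanned one?** Table S2 is the only place where both results are shown, so it can be checked there. The difference in change from the tabulated means is (day 180 − baseline, omega-3) − (day 180 − baseline, placebo).

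- Total omega-6: (25.8 − 25.0) − (28.3 − 26.9) = −0.60; stated −0.59.
- Omega-6:omega-3 ratio: (3.7 − 6.1) − (7.3 − 7.2) = −2.50; stated −2.54.

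The tabulated mean changes give −0.72 and −2.6, which are also close. The unplanned model is in effect the raw difference in change.

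**2. How far does it move the result?** Write the constrained estimate approximately as (day-180 difference) − b × (baseline gap), where b is the slope of day 180 on baseline. Then unconstrained − constrained = −(1 − b) × gap.

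| Outcome | Gap | Day-180 difference | Planned | Implied b | Predicted shift | Actual shift |
|---|---|---|---|---|---|---|
| Total omega-6 | −1.9 | −2.5 | −2.1 | 0.4/1.9 = 0.21 | +1.50 | −0.59 + 2.1 = +1.51 |
| Omega-6:omega-3 ratio | −1.1 | −3.6 | −3.5 | 0.1/1.1 = 0.09 | +1.00 | −2.54 + 3.5 = +0.96 |

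The shift has the opposite sign to the gap. For total omega-6 it takes p from 0.023 to 0.65, and the interval is (1.92 + 3.09)/(3.9 − 0.3) = 1.39 times as wide.

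**3. What might the planned threshold ratios be?** The documents do not give them. Assumptions: medians stand in for geometric means, and the log-scale slope b lies between 0.3 and 0.9. The planned ratio is then about 0.68 × (baseline ratio)^(1 − b).

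- Room: baseline ratio 0.47/0.30 = 1.57. Planned ratio 0.93 at b = 0.3, 0.71 at b = 0.9.
- Cooled: baseline ratio 0.43/0.32 = 1.34. Planned ratio 0.84 at b = 0.3, 0.70 at b = 0.9.

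A tentative slope can be recovered with log-scale SDs from IQR/1.349 (baseline variance v₁, day-180 variance v₂) and the change variance v_c from the printed CI with n = 21 and 19, using b = (v₁ + v₂ − v_c)/(2v₁).

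- Room: (0.187 + 0.501 − 0.435)/(2 × 0.187) ≈ 0.68, giving about 0.79 (0.53 to 1.17), p about 0.24.
- Cooled: (0.560 + 0.529 − 0.456)/(2 × 0.560) ≈ 0.57, giving about 0.77 (0.54 to 1.12), p about 0.17.

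Over b = 0.3 to 0.9 the approximate p-values run from 0.73 to 0.10 (room) and from 0.37 to 0.08 (cooled). If the cooled gap is taken from all three quartiles (ratio 1.59), its planned ratio could reach 0.94.

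**4. Significance as printed.** CNFD and CNBD both have p<0.001, so the thresholds rank third and fourth. Benjamini-Hochberg gives 0.077 × 4/4 = 0.077 for the cooled threshold. For room temperature it gives the smaller of 0.061 × 4/3 = 0.081 and 0.077, again 0.077. Neither passes 5%.

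**5. Was the trigger applied consistently?** Standardised baseline gaps (difference/pooled SD) from the tables:

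- Meibomian grading (Table S9): (1.63 − 1.00)/0.80 = 0.79, switched.
- Anterior blepharitis (Table S9): (1.48 − 1.08)/0.815 = 0.49, not switched.
- Total omega-6 (Table S2): (25.0 − 26.9)/3.85 = −0.49, given the sensitivity analysis.

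Two gaps of the same standardised size were treated differently. Without a stated criterion the selection cannot be verified.

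**The case against.** The deviation is disclosed in item 1 and marked on each affected estimate. The results tables provided are supplementary. The SAP's template for main Table 2 holds both thresholds with adjusted p-values, whereas Table S4 says its p-values are unadjusted, so it is not that table. The planned estimates may well be in the main report. All of this stands, and it limits the point to what Table S4 omits.

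The threshold figures are also soft. The room-temperature medians alone give (0.38/0.47)/(0.30/0.30) = 0.81, not the printed 0.68, so medians are an imperfect proxy for geometric means. That stands too: only the direction and rough size are usable.

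On consistency, item 1 speaks of imbalance in means or geometric means, not of standardised differences. The investigators may have used another scale, which is a reason to state it.

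Four stronger readings are tempting but unsupported.

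- **The unconstrained estimate is simply biased.** It is unbiased over randomisations and less precise; the shift is conditional on the observed gap.
- **The choice flips the threshold conclusions.** Both are non-significant as printed and probably under the plan. The documented flip is in total omega-6, a compliance marker, where the planned result is shown and the alternative is the less favourable one.
- **The SAP wording caused the switch.** The SAP does say that "the model will include treatment as the main factor and the treatment by study visit interaction", which coded literally would free the baseline means. But the planned values in Table S2 (−2.1, −3.5) differ clearly from the raw change differences, so the constrained model was in fact fitted.
- **The primary result is affected.** CNFL carries no imbalance mark, and its printed 2.70 lies between the day-180 difference (13.55 − 11.41 = 2.14) and the raw change difference (2.06 + 0.97 = 3.03), as a constrained estimate should.

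**Conclusion.** The point holds as an inconsistency in reporting. A model labelled as a sensitivity analysis is the only result shown in Table S4 for two of the four key secondary outcomes, and in these documents the planned estimate is missing. Given the baseline gaps, the printed ratio of 0.68 probably overstates the benefit relative to the plan: about 0.71 to 0.93 for room temperature and 0.70 to 0.84 for cooled. Those ranges rest on medians as proxies and an assumed slope of 0.3 to 0.9. The consequence is a larger effect and a more borderline p-value, not a changed decision at 5%. That the model is the raw difference in change, and that it can move a result materially, follows directly from Table S2 without those assumptions. The missing imbalance criterion is a separate gap and is certain.

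**What to change.** In Table S4, print the planned constrained estimate, CI and p-value for both central thresholds, with the Benjamini-Hochberg-adjusted p-value at day 180 as SAP Section 7 requires. Do the same, with unadjusted p-values, for the other outcomes marked as imbalance-adjusted in Tables S4, S8 and S9. Move the unconstrained results to footnotes labelled as sensitivity analysis, as in Table S2. State in item 1 what size of imbalance, on which scale, triggered the extra model.

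The SAP itself should not be edited now that results exist; any clarification of the model terms belongs in the changes section.

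The cost is re-tabulation, with at most a refit of the already specified model, and one added sentence. The downside for the investigators is that two key secondary estimates probably become less favourable to omega-3.

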2.4. Study population and entry criteria

2.4.1. Number of participants

A total of 50 patients will be randomised over the study duration.

Given a two-arm parallel design, with the pre-specified primary outcome of CNFL (taken as a continuous measure), for 80% power at a confidence level of 95%, using an estimated true difference between intervention arms of 2.9 units, mm/mm² (Chinnery *et al.*, 2017b), based on an expected standard deviation of 3.2 units, the required sample size is 21 participants per group. To allow for 15% participant attrition, the sample size within each group will be increased by this amount, giving a need to recruit a total of 25 participants in each interventions arm (n=50 for the trial).

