Michigan Diabetic Neuropathy Score (MDNS) composite score: clinical examination class	Categorical variables with 4 ordinal levels	1, 180	Ordered logistic regression model
Nerve conduction studies: Sural SNAP amplitude (Mid. lower leg-Lat. malleolus)		1, 180	Repeated measures model.
Nerve conduction studies: Peroneal CMAP velocity (Bl. knee – ankle)			
Nerve conduction studies: Tibial minimum F-wave latency (Ankle – Abd hal)			
Nerve excitability			
Median motor nerve excitability profile: TEd (10-20 ms)			Repeated measures model.
Median motor nerve excitability profile: TEd (peak)			
Median motor nerve excitability profile: TEd (90-100 ms)			
Median motor nerve excitability profile: TEh (90-100 ms)			
Median motor nerve excitability profile: Superexcitability		1, 180	
Median motor nerve excitability profile: Subexcitability			
Median motor nerve excitability profile: Resting I/V slope			
Median motor nerve excitability profile: strength duration time constant			
Safety			
Habitual visual acuity measured using a standard eye chart - Right eye		1, 30, 90, 180	Repeated measures model.
Habitual visual measured using a standard eye chart - Left eye		1, 30, 90, 180	
Intraocular pressure - Right eye		1, 180	Repeated measures model.
Intraocular pressure - Right eye		1, 180	

SAP version 1.4 30-06-2020 Page 29 of 40

Outcome	Distribution/Transformation	Days	Analysis model
Diabetic retinopathy grading - Worst eye retinopathy grading	Categorical variable with 4 ordinal levels	1, 180	Ordered logistic regression model
Diabetic retinopathy grading - Worst eye macular oedema grading	Categorical variable with 3 ordinal levels.		
Bloods: HbA1C (mmol/mol)		1, 180	Repeated measures model.
Bloods: cholesterol			
Bloods: HDL			
Bloods: LDL			
Bloods: folate			
Bloods: vitamin B-12			
Bloods: creatinine			
Compliance			
Omega-3 index		1, 180	Repeated measures model.
Omega-3: EPA concentration			
Omega-3: DHA concentration			
Omega-6 concentration			
Omega-9 concentration			
Omega-6:Omega-3 ratio			

SAP version 1.4 30-06-2020 Page 30 of 40

15. **Appendix** 4 LIST OF TABLES/FIGURES

Number	Title – analysis set
Table 1	Baseline participant characteristics (Intention-To-Treat sample)
Table 2	Central corneal nerve efficacy outcomes (Intention-To-Treat sample)
Table 3	Clinical neurophysiology outcomes (Intention-To-Treat sample), including secondary outcomes for small nerve fibre function and large nerve fibre function
Table 4	Compliance (Intention-To-Treat sample)

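### The fallback for MDNS class and the retinal grades (Fisher's test on sign of change) ignores ordering and describes no effect estimate or interval; supplement it rather than replace it

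*Combined protocol and SAP*

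**What the plan says.** SAP section 6 (Statistical procedures) states: "Categorical data will be analysed using an ordinal logistic regression model". It adds that the odds ratio between arms will be reported with a two-sided confidence interval. Appendix 3 assigns this model to the MDNS clinical class ("Categorical variables with 4 ordinal levels"), the worst-eye retinopathy grade and the worst-eye macular-oedema grade. MDNS is a secondary efficacy outcome under Aim 2. Retinopathy grading is a safety outcome under Aim 3.

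The section on changes from the planned analysis, item 2, reports that the model could not be fitted because of how the data were distributed within and between groups. In its place, "change from baseline at the study endpoint for each participant was categorised as negative change, positive change, or no change", and "Fisher's exact test was used to compare the proportions of participants between treatment groups". Item 2 mentions no effect measure or interval.

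Two other passages bear on this. SAP section 7.1.1 (Multiple testing) says: "All tests will be performed two-sided, and we will report two-sided 95% confidence intervals". It also says that, beyond the adjusted tests, findings will be interpreted on size, direction and interval width as well as p-values. Item 3 of the same list of changes deals with a failed model for OSDI by using a Wilcoxon rank-sum test with a Hodges-Lehmann estimate and 95% interval.

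**The concern.** Three things are lost in item 2, whatever the data look like.

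- **Order.** Fisher's test on a two-by-three table gives the same p-value however the three categories are labelled. Worse, unchanged and better are ordered, and for MDNS the question is directional.
- **Size of change.** A two-class change counts the same as a one-class change.
- **Estimate and interval.** A Fisher p-value says nothing about magnitude, direction or precision, which section 7.1.1 names as the basis for interpretation.

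The third loss matters most for the safety grades. With about 20 participants per arm, a non-significant p-value without an interval does not tell the reader whether a worsening was excluded or simply could not have been detected.

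**Working it through.** **The plan's own figure.** The only power calculation is for CNFL (protocol section 2.4.1), "using an estimated true difference between intervention arms of 2.9 units" and "based on an expected standard deviation of 3.2 units", with 80% power and two-sided 5%. The normal approximation gives n = 2(1.96 + 0.8416)² × (3.2/2.9)² = 19.1, so 20 per arm. The t-test solution is 20.12, so 21, as stated. 21/0.85 = 24.7, so 25, also as stated. No power is given for any ordinal outcome.

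**Inputs.** Day-180 numbers are 20 v 19 for limb tests (Tables S5 and S6), used as a proxy for MDNS, and 21 v 19 for corneal outcomes (Table S4), used as a proxy for the retinal grades. Category proportions are not in the documents; all those below are assumptions.

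**Method.** All pairs of three-category tables were enumerated. Let a_k and b_k be the omega-3 and placebo counts in category k, m_k = a_k + b_k, and N = n₁ + n₂.

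- Conditional probability of a table: Π C(m_k, a_k) / C(N, n₁).
- Fisher p: sum over tables with the same margins that are no more probable than the one observed.
- Exact rank p: W = Σ a_k r_k with midranks r_k; sum over tables with |W − n₁(N+1)/2| at least as large as observed.
- Power: total multinomial probability of tables with p ≤ 0.05.

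For a consistent shift, the placebo odds of better are multiplied by OR and the odds of worse divided by OR. Example, placebo 20/60/20% (worse/none/better) and OR 4: better odds 0.25 × 4 = 1, so 50%; worse odds 0.25/4 = 0.0625, so 5.9%; unchanged 44.1%.

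**Consistent shift, 20 v 19 (power, %)**

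| Placebo worse/none/better | OR | Fisher | Exact rank | Difference |
|---|---|---|---|---|
| 5/90/5 | 4 | 13.1 | 13.9 | +0.8 |
| 10/80/10 | 4 | 32.0 | 34.0 | +2.0 |
| 15/70/15 | 4 | 41.3 | 46.6 | +5.3 |
| 20/60/20 | 4 | 46.3 | 53.6 | +7.3 |
| 33/33/33 | 5 | 60.7 | 69.2 | +8.5 |

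Over OR 2 to 10, with 10% to 67% of placebo participants changing grade, the difference runs from −0.2 to +8.5 points at 20 v 19, and from 0.0 to +10.0 at 21 v 19.

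**Other patterns (power, %; Fisher then exact rank)**

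| Omega-3 v placebo, worse/none/better | 20 v 19 | 21 v 19: rank minus Fisher |
|---|---|---|
| 30/70/0 v 5/95/0 (worsening only) | 45.9, 45.9 | 0.0 |
| 25/73/2 v 3/95/2 (one tail shifts) | 41.6, 33.7 | −7.9 |
| 30/65/5 v 5/90/5 (one tail shifts) | 48.3, 35.4 | −12.6 |
| 25/55/20 v 5/90/5 (both tails widen) | 59.4, 7.1 | −54.4 |

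Both tests give the same p-value if worse and better are swapped. The one-tail losses therefore apply equally when only the share improving rises, which is a possible pattern for MDNS. With no effect at 20/60/20% in both arms (20 v 19), the rejection rates are 4.6% (Fisher) and 3.8% (rank).

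**What an interval would add.** Suppose none of 21 omega-3 participants worsened. The exact 95% upper limit for that arm alone is 1 − 0.025^(1/21) = 16.1%. A Fisher p-value near 1 would not show this.

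**The case against.** The strongest reply is that the switch was disclosed with a reason, that these outcomes were never powered and carry unadjusted p-values, and that the SAP already promises cautious reading. All of that stands, and the primary CNFL analysis is not touched.

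A reader might infer that Fisher's test costs this trial a fixed amount of power, say 7 to 8 points, and should be replaced by a rank test for all three outcomes. The documents do not support this. A gain of that size needs roughly 40% or more of placebo participants to change grade, together with a sizeable consistent shift. If few change, the gain at 20 v 19 is about 0 to 3 points. Few changes is itself an assumption, though it would fit the reported failure of the ordinal model.

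For the safety grades the replacement could do harm. A rank score lets improvements offset worsening, and Aim 3 asks about change in retinopathy grading without fixing a direction. Nor does the OSDI fallback settle the matter: OSDI is a 0 to 100 score, not a grade with a few levels.

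A reader might also infer that no estimate was ever reported. The supplementary tables supplied contain no results for these three outcomes, so this cannot be checked. Ocular surface staining (Table S9) and eGFR category (Table S10) appear with p-values and no estimate.

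What survives is that item 2 describes neither an ordered analysis nor an interval, and section 7.1.1 depends on the latter.

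**Conclusion.** The point holds as a modest, cheap improvement. Item 2 discards the ordering and describes no estimate or interval, where the SAP had promised an odds ratio with one. That follows from the text alone and needs no assumption about the data.

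The power consequence has no single value. At 20 or 21 v 19, an exact ordered test gains about 0 to 10 points under a consistent shift. It gains nothing if there is only worsening, loses about 8 to 13 points in the worked cases where one tail shifts and a few participants move the other way, and loses 50 or more if both tails widen. These figures rest on assumed proportions, on proxy sample sizes, and on tests applied to the three sign categories. Power for a test on the number of classes changed was not computed. The case for acting is therefore the missing direction and precision, not a promised gain in power.

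**What to change.** Keep the Fisher results as disclosed and keep the improved/unchanged/worsened counts. Add the following to item 2.

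- **MDNS class:** an exact Wilcoxon (permutation) test on the signed number of classes changed, using the class as item 2 defines it. Report the probability that an omega-3 participant has the better change, counting ties as one half, with a 95% confidence interval. Label this supplementary and post hoc, since the data are already unmasked.
- **Retinopathy and macular-oedema grades:** retain Fisher's test and add the between-arm difference in the proportion worsening, with an exact 95% confidence interval. Do not substitute a rank score.

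The cost is a few lines of code and a sentence or two per outcome. The downside is a little more post-hoc analysis, and a rank test for MDNS that is weak if one arm has both more improvement and more worsening. The counts, shown alongside, would reveal that pattern.
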